8.3. IGF-1 SDS

A descriptive table including the number and percentages of subjects by visit will be presented where:

- IGF-1 SDS > 2.0
- IGF-1 SDS > 3.0

Listings of IGF-1 and IGF-1 SDS for subjects with abnormally high IGF-1 SDS will be generated.

8.4. Clinical Laboratory Evaluations

Descriptive summaries of actual (absolute) values and changes from extension study baseline values if applicable will be presented in the tables for the following by visit for the full analysis set:

- Chemistry: sodium, potassium, calcium, phosphate, chloride, total bilirubin, alkaline phosphatase, lactate dehydrogenase (LDH), aspartate aminotransferase (AST), alanine aminotransferase (ALT), gamma glutamyl transferase (GGT), albumin, total protein, creatinine, urea nitrogen, uric acid, serum iron and transferrin
- Hematology: hemoglobin, leukocytes, differential blood count of leukocytes, platelet count
- Hormone Levels: thyroid status (TSH, fT4, and fT3 levels) and morning cortisol
- Glucose Metabolism: HbA1c.
- Lipid Metabolism: Total cholesterol, triglycerides, HDL and LDL

Laboratory values will also be displayed in the data listings and those that are outside the normal range will be flagged, along with corresponding normal ranges. Any out-of-range values that are identified by the investigator as being clinically significant will be presented in a data listing.

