9.6.2. Stopping/Dose Reductions

The investigator or Medical Expert (and, if needed, with the ISC review) may stop or reduce the dose of investigational product for an individual subject at any time during the trial (please notify the Medical Expert as soon as possible). For example, consideration for stopping or reducing the dose may occur in the presence of the following symptoms and laboratory abnormalities:

- Severe hGH-related AEs at any time during the trial (eg, peripheral edema, severe headache, intracranial hypertension or other adverse drug reaction and/or abnormal laboratory values).
- Pregnancy: A subject must be discontinued from the trial if pregnant.
- IGF-1 > +2.0 SDS: The TransCon hGH dose may be decreased by approximately 20% to the next lower weight bracket, unless a different target SDS is identified in consultation with the Medical Expert. See Section 9.3 for details. (Although the prior *requirement* has been eliminated for a second [“confirmatory”] IGF-1 SDS test prior to dose titration, a second IGF-1 SDS test collected 5 days post-dose (± 1 day) remains optional at the investigator’s discretion.)

Any re-establishment of the prior dose due to a subsequent sub-optimal IGF-1 response should receive prior approval by the Medical Expert.

- In those subjects who have historically been dose titrated to a bracket different than expected for weight, the investigator may—at study visits—recommend maintenance of the current absolute dose until the visit’s IGF-1 SDS values are available. Once the IGF-1 SDS values are available, the investigator may then select the most appropriate dose volume or DCC presentation.
- Evidence of hypersensitivity to TransCon hGH
- Evidence of clinically significant pre-diabetes or diabetes (HbA1c > 6.2% and an absolute increase of 0.5% from the prior visit HbA1c): Confirmation of HbA1c level is required. Once confirmed, TransCon hGH dose may be decreased to the next lower weight bracket. If appropriate follow-up monitoring shows progressively worsening glucose intolerance, additional TransCon hGH dose adjustments may be appropriate.
- Clinical evidence of BIH based on history and physical exam, including visual changes, headaches, nausea, vomiting, and/or papilledema on funduscopy: TransCon hGH treatment should be discontinued while BIH is clinically managed.

Reinstitution of TransCon hGH treatment, preferably at a lower dose, should receive prior approval by the Medical Expert.

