7. Pubertal status assessment (Tanner stage)
8. Blood collection for the following laboratory assessments*:
 - IGF-1 and IGFBP-3
 - Antibodies against hGH and PEG
 - If warranted, TransCon hGH, hGH, and PEG serum levels may be analyzed for the interpretation of immunogenicity titers
 - mPEG

- Hormone/glycemic Status (TSH, FT4, FT3, morning cortisol, and HbA1c)
- Chemistry
- Hematology
- Lipid panel
- **Females of child-bearing potential only:** hCG
*Fasting not required. Banked blood samples may be used for additional characterization of anti-drug antibody responses.

9. Investigational product dose adjustment, as needed

10. Investigational product & subject diary dispensing

An overview of all visits is provided in the Schedule of Events, Section 18.2.

10.2.2.4. Patient-Reported Outcome Completion (6th week after transition to the GH Auto-Injector) and Device Usability Questionnaire

For all subjects who have transitioned to the GH Auto-Injector (6th week of GH Auto-Injector Use): Immediately prior to the 6th dose of the GH Auto-Injector, and at the next scheduled clinic visit (approximately 13 weeks after transition to the GH Auto-Injector), patient-reported outcomes questionnaires will be completed by subjects/parents/legal guardians/caregivers, as applicable. At 6 weeks after transition to the GH Auto-Injector, the questionnaires will be completed in the subject diary. At the next scheduled clinic visit (approximately 13 weeks after transition to the GH Auto-Injector), the questionnaires will be completed at the clinic visit, prior to review of the subject diary, AEs, and concomitant medications. The questionnaires are:

- C&OS-P
- CSDS-P
- **CSDS-C: only for subjects ≥ 9 years old (at time of transition to GH Auto-Injector)**

In addition, on the day of the 6th dose using the GH Auto-Injector (either immediately before or after the 6th dose) and at the next scheduled clinic visit (approximately 13 weeks after transition to GH Auto-Injector), the following questionnaire will be completed by the individual primarily responsible for preparing and performing the injection with the GH Auto-Injector.

- DUQ

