12. ADVERSE EVENTS, SERIOUS ADVERSE EVENTS, AND REPORTING

12.1. ADVERSE EVENTS

12.1.1. Definition

An AE is defined as any untoward medical occurrence in a clinical investigation subject administered a pharmaceutical product and which does not necessarily have a causal relationship with the treatment. An AE can therefore be any unfavorable and unintended sign, symptom, or

disease temporally associated with the use of a medicinal (investigational) product, whether or not related to that product. An AE can arise with any use (eg, in combination with another drug), route of administration, formulation, or dose, including an overdose.

Possible AEs associated with TransCon hGH are listed in the Investigator's Brochure or the accompanying Reference Safety Information. The adverse reactions associated with commercially available daily hGH-containing products that may or may not be observed with use of TransCon hGH are:

- Sudden death in pediatric patients with Prader-Willi syndrome; risk factors include morbid obesity, history of upper airway obstruction or sleep apnea, and unidentified respiratory infection
- Intracranial tumors, particularly meningiomas, in teenagers/young adults treated with brain irradiation as children
- Injection site reactions/rashes (as well as rare, generalized hypersensitivity reactions)
- Skin atrophy and lipoatrophy
- **Note:** Rotating the injection site (see Section 9.3) is expected to decrease the risk of skin atrophy or lipoatrophy.
- Headaches
- Glucose intolerance, including impaired glucose tolerance/impaired fasting glucose as well as overt diabetes mellitus
- Intracranial hypertension with papilledema, visual changes, headache, nausea, and/or vomiting
- Fluid retention manifested by edema, arthralgia, myalgia, nerve compression syndromes (including carpal tunnel syndrome/paresthesias)
- Hypothyroidism (central [secondary] hypothyroidism may first become clinically evident or worsen in patients with GHD during hGH treatment)
- Slipped capital femoral epiphysis (occurs more frequently in patients with endocrine disorders or in patients undergoing rapid growth)
- **Note:** Any subject with the onset of a limp or complaints of hip or knee pain should be carefully evaluated for a slipped capital femoral epiphysis.
- Progression of pre-existing scoliosis due to rapid growth (hGH has not been shown to increase the occurrence of scoliosis)

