Any change from baseline health status that meets the above AE definition and occurs from the time of the first administration of investigational product until the completion of the study or the Early Termination Visit will be recorded as an AE.

Out-of-range laboratory values or test results may constitute AEs if they:

- induce a new/worsening diagnosis, clinical sign, or symptom, or
- require therapy.

Routine titration of chronic, concomitant medications (eg, increase of levothyroxine dose due to interval weight gain and without associated signs/symptoms of overt hypothyroidism) would not be considered as AEs. Whenever possible, an AE should be recorded as a specific diagnosis or syndrome rather than as a sign, symptom, or out-of-range laboratory value. If there is not a diagnosis, the event term should be the clinical sign or symptom. Based on an investigator’s clinical judgement, multiple concurrent symptoms should be grouped together as a single, unifying diagnosis (e.g. headache, fever, cough, and coryza constitute a probable viral upper respiratory tract infection, and this single AE term is more appropriate than listing each symptom as a separate AE).

Care should also be taken to record the most medically appropriate term (eg, hypertension for elevated blood pressure that persists and requires chronic treatment and follow-up, or increased blood pressure for elevated blood pressure that occurs for a limited time and does not persist or require ongoing treatment).

AEs will be documented at the maximum intensity experienced. If a previously recorded AE or condition recorded as part of medical history increases in severity or frequency, it will be recorded as a new AE.

All AEs will be considered ongoing until they have completely resolved or, in the case of a condition recorded as part of medical history, returned to baseline status prior to investigational product administration. At study completion or the Early Termination Visit, all AEs should have a statement regarding resolution.

Any SAE that is determined to be related to the investigational product will be followed until resolution or stabilization.

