14.1. TRIAL ENDPOINTS

14.1.1. Safety Endpoints

The safety endpoints as measured throughout the long-term dosing of weekly TransCon hGH treatment include the following:

- Incidence of AEs
- Incidence of antibodies against hGH, including neutralizing antibodies
- Incidence of antibodies against PEG
- Incidence of antibodies against TransCon hGH
- Incidence of IGF-1 SDS > 2.0, > 3.0
- Parameters of HbA1c and lipids
- Hormone levels, including thyroid status and morning cortisol
- All other hematology and chemistry parameters
- Vital sign measurements

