4.2. Final Analysis

All final, planned analyses identified in this SAP will be performed after the last subject has completed the last study visit and end of study assessments, and all relevant study data have been processed and integrated into the analysis database.

5. General Statistical Considerations

All analysis will be performed based on full analysis set and summaries will be presented overall and for subjects rolling over from Study CT-301 and Study CT-302 TransCon hGH group and Genotropin group separately. Descriptive summaries will be provided where appropriate for each of the primary and secondary variables.

Continuous, quantitative (absolute values at each time point and change from baseline if applicable) variable summaries will include the number of subjects (n) with non-missing values, mean, standard deviation (SD), standard error (SE), median, minimum, and maximum, unless otherwise specified.

Categorical, qualitative, variable summaries will include the frequency and percentage of subjects who are in the particular category. In general, the denominator for the percentage calculation will be based upon the total number of subjects in the study population for the cohorts, unless otherwise specified.

All data collected on eCRF will be presented in listings.

All analysis will be performed using SAS® Software version 9.4 or later.

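### SAP 8.4 specifies no count of children who cross an HbA1c threshold at any time, although the protocol names glucose intolerance as an hGH reaction and states its own HbA1c criterion

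*SAP*

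**What the plan says.** Long-term safety is the primary objective (Protocol 6.1, SAP 2.1). Protocol 12.1.1 lists among the reactions of daily hGH products "Glucose intolerance, including impaired glucose tolerance/impaired fasting glucose as well as overt diabetes mellitus". The safety endpoints in Protocol 14.1.1 include "Parameters of HbA1c and lipids".

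Blood for glycaemic status is drawn every 26 weeks. Protocol 10.2.2.3 names HbA1c and no other glycaemic test in that group. SAP 8.4 has one line for it, "Glucose Metabolism: HbA1c", and its itemised chemistry list contains no glucose. The planned output is: "Descriptive summaries of actual (absolute) values and changes from extension study baseline values if applicable will be presented in the tables", by visit. SAP Section 5 defines those summaries as n with "mean, standard deviation (SD), standard error (SE), median, minimum, and maximum". Out-of-range values are flagged in listings, and values the investigator calls clinically significant go to a listing.

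Protocol 9.6.2 gives a numeric description of clinically significant pre-diabetes or diabetes: HbA1c above 6.2% together with an absolute increase of 0.5% from the prior visit's HbA1c, with confirmation required. It adds: "Once confirmed, TransCon hGH dose may be decreased to the next lower weight bracket".

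On adverse events, Protocol 12.1.3 says: "Out-of-range laboratory values or test results may constitute AEs if they" induce a new or worsening diagnosis, sign or symptom, or require therapy. Events judged mild and unrelated are not recorded, apart from site-specific preferences (Protocol 12.1.1).

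**The concern.** A glycaemic harm concerns individual children who cross a level, and a few such children barely move a group mean. The natural summary is how many of the children tested ever crossed it. The SAP takes that approach for IGF-1 SDS, where Section 8.3 tabulates numbers and percentages above 2.0 and 3.0. It does not do so for HbA1c, although the protocol supplies a criterion that could be counted.

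Without a count, the report has no numerator or denominator for this harm except what reaches the adverse event tables, and that depends on investigator judgement. A child whose HbA1c rose without symptoms, and for whom no diagnosis was recorded and no therapy given, need not appear there. For a trial whose purpose is long-term safety, the reader would have to assemble the incidence by hand from listings.

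**Working it through.** The plan has no figure of its own to reproduce here: the trial is descriptive and its size is set by the parent trials. The check has two parts.

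**1. Could any planned output supply the count?**

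- *By-visit table (SAP 8.4, Section 5).* The maximum shows the single worst retained value at a visit. One child at 6.5% and eight children at 6.5% give the same maximum.
- *Window rule (SAP 5.3).* Unscheduled tests are mapped to the nearest scheduled visit, and one value per window is kept, the one closest to the target day. An invented example: Visit 3 has target day 181 and window 136 to 226. A scheduled HbA1c of 6.6% on day 170 is 11 days from target; a repeat of 6.1% on day 184 is 3 days from target. The repeat is kept and the 6.6% leaves the by-visit table. With other dates the repeat is the value lost.
- *Shift tables.* SAP 5.3 says in passing that shift tables use all data points. None is defined for HbA1c or any other parameter.
- *TEAE tables (SAP 8.1).* These count subjects by SOC and preferred term, but only for events recorded as AEs. No glycaemic grouping of terms is planned.
- *Dose-change table (SAP 8.6).* It counts subjects with reduced doses, without the reason.
- *Listings.* They show individual cases, with no number or percentage.

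No specified output gives the number of children above any HbA1c level.

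**2. How many cases could the mean absorb? (Illustration)**

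From the documents: N about 300 (Protocol 8) or about 400 (SAP 3.2). Assumed, because the documents give neither: SD of HbA1c change 0.3 points, range 0.2 to 0.4; each case rises by 1.2 points (5.3% to 6.5%). The other children are taken to change by zero on average, and all cases are raised at the same visit.

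Half-width of the 95% interval for the mean change = 1.96 × SD / √N. Shift in the mean from k cases = 1.2 × k / N.

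| N | SD | Half-width | Shift per case | Largest k inside half-width |
|---|---|---|---|---|
| 300 | 0.2 | 0.0226 | 0.0040 | 5 |
| 300 | 0.3 | 0.0339 | 0.0040 | 8 |
| 300 | 0.4 | 0.0453 | 0.0040 | 11 |
| 400 | 0.2 | 0.0196 | 0.0030 | 6 |
| 400 | 0.3 | 0.0294 | 0.0030 | 9 |
| 400 | 0.4 | 0.0392 | 0.0030 | 13 |

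For example, at N = 300 and SD 0.3, 0.0339 / 0.0040 = 8.5, so 8 cases. Six cases would move the mean by 6 × 0.0040 = 0.024 points. As a count they would read 6/300 = 2.0%, exact 95% CI 0.74% to 4.30% (at N = 400: 1.5%, 0.55% to 3.24%). Zero cases would also be informative: the one-sided 95% upper bound is 0.99% at N = 300 and 0.75% at N = 400.

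The masking has a limit. Fifteen cases in 300 (5%) rising by 1.0 point shift the mean by 0.050, which exceeds 2 SE even at SD 0.4 (2 × 0.0231 = 0.046).

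**The case against.** The strongest reply is that these children are not lost. A new or worsening diagnosis is a separate route to an AE and needs neither symptom nor therapy. Protocol 9.6.2 itself describes its criterion as evidence of pre-diabetes or diabetes, so a confirmed case may well be recorded as a diagnosis and counted among the TEAEs. The exemption for laboratory values without a sign or symptom covers IGF-1 and IGFBP-3, not HbA1c. SAP 8.1 also still includes abnormal laboratory findings in its AE definition. This largely stands, and it rules out an inference a reader might draw, that such children are counted in no table. It does not close the gap. The protocol says such values may be AEs, which leaves the decision to the investigator. The SAP wording belongs to a plan written to Protocol 1.0, whereas the current protocol's definition omits that phrase and governs what sites record.

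A reader might also infer that only means are planned, or that the trial could report no glycaemic change at all. Neither is supported. The maximum and maximum change would show a high retained value, listings flag it, and a later fall does not erase an earlier visit's summary.

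Nor does the SAP depart from its endpoint. The protocol uses the word incidence for AEs, antibodies and IGF-1 SDS, but not for HbA1c, and Protocol 14.4 asks for descriptive statistics. The 9.6.2 criterion guides dose decisions and is not an endpoint. The count is an improvement to the plan.

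Finally, no inference on the mean is planned, and SD, rise and case number are assumed, so the arithmetic shows scale only. The protocol's chemistry panel is not itemised, so the claim about a single glycaemic measure is limited to the SAP.

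**Conclusion.** The point holds in this form: for HbA1c the SAP specifies by-visit descriptive statistics and flagged listings, and no number or percentage of children crossing a threshold at any time. Cases recorded as AEs will be counted as TEAEs. Cases not so recorded, because there was no diagnosis, sign, symptom or therapy or because the event was judged mild and unrelated, can be identified individually only in listings. The by-visit maximum is one value and may omit unscheduled, confirmatory or even scheduled peaks under the SAP 5.3 rule.

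The size depends on assumptions the documents cannot confirm. At N = 300, with an SD of 0.3 (0.2 to 0.4) and a 1.2-point rise, the mean can absorb 8 (5 to 11) cases; at N = 400, 9 (6 to 13). The absence of a count does not depend on those assumptions. This is a change the SAP should make, given the primary objective; it does not undermine the trial.

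**What to change.** In SAP 8.4 add one table, by parent-study group and overall. The denominator is subjects with at least one post-baseline HbA1c. Give the number and percentage who at any time in the extension, at a scheduled or unscheduled test, had:

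- (a) HbA1c above 6.2%;
- (b) the Protocol 9.6.2 criterion, with confirmation status where a repeat test is recorded.

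Both rows are needed. A path of 5.5%, 5.9%, 6.3% passes 6.2% in steps of 0.4 and so meets (a) without meeting (b). Because HbA1c is drawn only at alternate visits, the SAP should state which earlier value serves as the prior one for (b), agreed with the clinical team.

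Add a shift from baseline to highest post-baseline value at the same cut-point, using all data points and not the windowed ones. Flag subjects on diabetes treatment, which is a permitted and recorded concomitant medication; children with diabetes may enter if HbA1c is below 8.0% and they have no diabetic complications.

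The cut-point is the protocol's own, used here only for tabulation; no dosing rule is proposed. The cost is SAP wording and one extra table, with no new assessments. Confirmation can be shown only as far as repeat tests are identifiable in the database. The reported safety result may look slightly less favourable.

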9.9.2.1. Permitted Therapies

1. Replacement therapy for other non-GH pituitary deficiencies. As hGH may enhance the transformation of hydrocortisone to cortisone, the investigator may increase the dose of hydrocortisone replacement therapy if needed (eg, for anticipated stress).
2. Treatment for diabetes
3. Over-the-counter vitamins, minerals, or other dietary supplements only if their use is agreed to by the investigator.

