5.5. Analysis Population

The Full Analysis Set includes all subjects who signed inform consent for this study and received at least one dose of study drug during the trial. The efficacy and safety analysis will be performed based on full analysis set.

6. Subject Disposition

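### Thyroid and cortisol safety is tabulated only as pooled by-visit summaries, with no count of new out-of-range values or new replacement starts

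*SAP*

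**What the plan says.** Long-term safety is the primary objective (Protocol 6.1), and "Hormone levels, including thyroid status and morning cortisol" is a listed safety endpoint (Protocol 14.1.1). Among the reactions known for daily hGH that may also occur here, Protocol 12.1.1 includes "Hypothyroidism (central [secondary] hypothyroidism may first become clinically evident or worsen in patients with GHD during hGH treatment".

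Protocol 9.9.2.1 permits "Replacement therapy for other non-GH pituitary deficiencies", and Protocol 12.1.3 uses levothyroxine as its example of a chronic concomitant drug. Users are therefore expected, although neither document says how many. Hormones are sampled at Visit 1 and then every 26 weeks (Protocol 10.2.2.3 and 18.2).

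For the laboratory tables, SAP 8.4 states: "Descriptive summaries of actual (absolute) values and changes from extension study baseline values if applicable will be presented in the tables". The list includes "Hormone Levels: thyroid status (TSH, fT4, and fT3 levels) and morning cortisol". The statistics, set in SAP Section 5, are the number of non-missing values and "mean, standard deviation (SD), standard error (SE), median, minimum, and maximum, unless otherwise specified".

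On the population, SAP 5.5 states: "The efficacy and safety analysis will be performed based on full analysis set". The standing split in SAP Section 5 is by parent study and prior treatment: "summaries will be presented overall and for subjects rolling over from Study CT-301 and Study CT-302 TransCon hGH group and Genotropin group separately". The optional subgroups in SAP 9.4 do not include replacement status, and laboratory values are not among the variables named there.

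**The concern.** The endpoint is at its most informative when a child who was not deficient becomes so. The planned table handles that event poorly in two ways.

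- **Dilution.** A few low values are averaged with those of several hundred children, some of whose values reflect a replacement dose rather than their own hormone production.
- **Loss over time.** A deficiency that is found is likely to be treated. Once the value is back in range, later visits show little or no change for that child.

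A flat row of means could then be read as reassurance about thyroid function when it says little about how many children developed a deficiency. Because change is taken from the extension baseline, a deficiency that appeared and was treated during the parent trial is already inside that baseline.

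**Working it through.** The plan states no figure on this point, so there is nothing to reproduce. The check has two parts: an illustration of what the mean can show, and a reading of the other outputs.

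**1. How far the mean moves**

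From the documents: N is about 300 (Protocol Section 8) or about 400 (SAP 3.2). Assumed, not in the documents: 2%, 5% or 10% of children have new, untreated low fT4 at the same visit; their fall is 1.5 to 2.5 SD; treatment returns the value to normal; nothing else changes.

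- Shift in the mean, in SD units = k × fall / N, where k is the number of cases.
- Standard error of the mean, in SD units = 1/√N = 1/√300 = 0.058.

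| New cases (N = 300) | k | Shift in mean (SD) | Shift in SE | Direct count |
|---|---|---|---|---|
| 2% | 6 | 6×1.5/300 = 0.03 to 6×2.5/300 = 0.05 | 0.5 to 0.9 | 6 |
| 5% | 15 | 15×1.5/300 = 0.075 to 15×2.5/300 = 0.125 | 1.3 to 2.2 | 15 |
| 10% | 30 | 30×1.5/300 = 0.15 to 30×2.5/300 = 0.25 | 2.6 to 4.3 | 30 |

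If half the cases are already treated and normal at that visit, each shift halves. If all are, it is zero. With N = 400 the shifts in SD units are the same and the standard error is 1/√400 = 0.050. Putting all cases at one visit favours the mean, since real cases would be spread over visits 26 weeks apart.

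**2. Is pooling or averaging the main problem?**

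Assume that 20% to 40% of 300 children are already on replacement, that 5% of the remaining 240 to 180 become deficient (12 to 9 children), and that their fT4 falls by 4 pmol/L.

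- Pooled mean: 12×4/300 = 0.16 and 9×4/300 = 0.12 pmol/L.
- Off-replacement children only: 12×4/240 = 9×4/180 = 0.20 pmol/L.

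Splitting gains 0.04 to 0.08 pmol/L. The larger weakness is using a mean where a count is needed.

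**3. Do other outputs supply the count?**

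- *TEAE tables (SAP 8.1).* Protocol 12.1.3 says that an out-of-range result leading to a diagnosis or needing therapy may be an AE. Protocol 12.1.1 and 12.1.3 leave out events that are both mild and unrelated (12.1.1 allows for site reporting preferences), and the definition of mild in 12.1.2.1 does not rule out a need for intervention. Capture is therefore likely in many cases but not assured.
- *Medication tables (SAP 7.3).* Prior means started before the first extension dose; concomitant means taken on or after it. A long-term levothyroxine user is in both. A new starter is in the second, together with existing users. Subtracting one from the other is unreliable, because prior includes drugs already stopped and incomplete dates can default to both classes. Neither table has the at-risk denominator.
- *Listings (SAP 8.4).* Out-of-range values are flagged, but with no incidence and no link to the start of replacement.
- *Shift tables.* SAP 5.3 mentions them in the visit-window rule, but SAP 8.4 specifies none. By contrast, SAP 8.3 does count children above IGF-1 SDS thresholds.

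**The case against.** The strongest reply is that SAP 8.4 is only one part of the safety plan. AE incidence is the first safety endpoint in Protocol 14.1.1. Hypothyroidism is on the protocol's own list of hGH reactions, which makes it less likely that an investigator would call a new case unrelated. The exemption for routine levothyroxine titration concerns children already treated. Medication dates are collected and listed, so nothing is lost; it is only not tabulated. The trial is descriptive, with no hypothesis to protect.

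Much of this stands, and it rules out stronger readings that a reader might draw.

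- *That a case vanishes from the table as soon as it is treated.* It does not. The abnormal value stays in the row of the visit where it was measured, where it can set the minimum or maximum, and it stays in the listing.
- *That the plan cannot detect hypothyroidism.* It can, through TEAEs and listings, though incompletely. At 10% incidence even the mean would move visibly before treatment.
- *That off-replacement children, classified at each sample, should form the safety table.* A newly treated child would leave that group, and later visits would again show only unaffected children. It would also sideline children already on replacement, although Protocol 12.1.1 names worsening as well as first appearance.
- *That cortisol and HbA1c raise the same problem with the same support.* The documents do not say that hGH unmasks cortisol deficiency; Protocol 9.9.2.1 speaks only of an effect on hydrocortisone conversion. Diabetes is a listed reaction with its own AE route.

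The reply does not supply an incidence of new deficiency or of new replacement starts among children at risk. No planned output gives one.

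**Conclusion.** The concern holds in a limited form. SAP 8.4 reports a named safety endpoint in a way that is weak for the one thyroid risk the protocol describes. New hypothyroidism is diluted in the mean when measured and no longer shows at later visits once normalised. The other outputs may reveal individual cases, but they do not count new replacement starts against the children at risk.

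Under the assumed rates of 2% to 5% in 300 children, the mean fT4 moves by 0.03 to 0.125 SD (0.5 to 2.2 standard errors), where a count would show 6 to 15 children. These sizes rest on assumed incidence and fall. The share of children on replacement is not stated, so the actual dilution is unknown. The finding calls for better tabulation. It does not show that safety information is missing from the database.

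**What to change.** Amend SAP 8.4 as follows.

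1. Among children not on levothyroxine at the first extension dose, report the number and percentage who later start it. Do the same for glucocorticoid replacement. Derive this from the first start date of the drug, so that a dose-change record is not taken for a new start, and use the recorded indication to separate replacement from other glucocorticoid use.
2. Report shift or ever-out-of-range counts for TSH, fT4, fT3 and morning cortisol against the normal range. For children not on replacement at extension baseline, use only values before any new replacement start.
3. Show the by-visit summaries by replacement status fixed at extension baseline, not at the time of the sample. Keep the on-replacement group visible, because worsening is also a named risk.

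A parallel count of new diabetes-treatment starts beside HbA1c is optional.

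The cost is SAP wording, one derivation from medication dates already on the eCRF, a few extra tables, and smaller numbers in each group. No visit, sample or treatment rule changes.
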